11.3.1.1 FWCS - Fitzpatrick Wrinkle Classification System

11.3.1.2 GAIS - Global Aesthetic Improvement Scale Assessment

11.3.1.3 WAS - 5-point Wrinkle Assessment Scale

11.3.1.4 Subject Experience

11.3.1.5 Pain Level VAS Scale

11.3.1.6 Subject Subjective Downtime Assessment

11.3.1.7 Subject Response Questionnaire (redness, edema and crust - time to resolve)

11.3.1.8 End-User Experience Assessment

11.3.1.9 Repeated measures or Friedman's test (as is appropriate) will be applied for analyzing the changes within side (device) and .The two-sample T-test or Non-parametric Mann-Whitney Rank test (as is appropriate) will be applied for comparative analysis of the changes between the devices.

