The following assessment method will be applied by the blinded assessors (by images only):

- FWCS - Fitzpatrick Wrinkle Classification System

2.4.Secondary Outcome Endpoints

The following criteria will be assessed as secondary outcome endpoints:

- Secondary Effectiveness/Performance shall be assessed and quantified by a handling physician (one of the team's investigators of the study).

The following assessment methods will be applied (frontal clinical assessment or by images):

- FWCS - Fitzpatrick Wrinkle Classification System
- GAIS - Global Aesthetic Improvement Scale Assessment
- WAS - 5-point Wrinkle Assessment Scale
- Subject Experience
- Pain Level VAS Scale
- Subject Subjective Downtime Assessment

- Subject redness, edema and crust assessment (time for resolution)
- End-User Experience Assessment

Clinic Visits Baseline, 4wk, 8wk, (optional 12wk and 16wk), 20wk, 28wk, 42wk

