5. SUBJECT SELECTION: NUMBER OF SITES/INVESTIGATORS

There will be two investigational sites participating in this study, including one site in the U.S. and one in Israel.

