5.1. Number of Subjects

A total of 82 subjects will be recruited to the study. They will be randomly split to two separate arms (41/arm) in each site, and undergo periorbital fractional treatments.

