9. STUDY FLOWCHART AND FOLLOW-UP ASSESSMENTS

Procedure	Visit 1	Visit 2	Visit 3	Visit 4	Visit 5	Visit 6	Visit 7	Visit 8
	Treatment 1 ^c	Treatment 2	Treatment 3	Treatment 4 Optional	Treatment 5 Optional	1 month Follow-up 1	3 months Follow-up 2	6 months Follow-up 3
	T ₀ ^f (± 5d) ± Δ ^{ef}	T ₀ + 4w (± 5d) ± Δ	T ₀ + 8w (± 5d) ± Δ	T ₀ + 12w (± 5d) ± Δ ^e	T ₀ + 16w (± 5d) ± Δ ^e	T ₀ + 20w (± 8d) ± Δ ^e	T ₀ + 28w (± 8d) ± Δ ^e	T ₀ + 42w (± 8d) ± Δ ^e
Max duration	-	4w+5d	8w+10d	12w+15d	16w+20d	20w+25d	28w+33d	40w+41d ~ 47w
Min duration	-	4w-5d	8w-10d	-	-	12w-15d	20w-23d	32w-29d ~28w
Subject Screening, Enrolment Procedure & Informed Consent ^g , Post treatment care instructions	X							
Facial dermatological skin examination	X	X	X	X	X	X	X	X
Inclusion/ Exclusion criteria	X							
Medical/Surgical history	X							
Demographics	X							
Limited Physical examination ^a	X							
Concomitant Therapy/Medication	X _b	X	X	X	X	X	X	X
Verbal Inquiry regarding pregnancy	X	X	X	X	X	X	X	X
Photography of Treatment Area(s) – prior to treatment	X (baseline)	X	X	X	X	X	X	X
Photography of Treatment Area(s) – After treatment			X					
Investigational/Comparator Device Treatment	X	X	X	X	X			
Subject experience and satisfaction questionnaire	X		X*	X*	X*	X*		X

Procedure	Visit 1	Visit 2	Visit 3	Visit 4	Visit 5	Visit 6	Visit 7	Visit 8
	Treatment 1 ^c	Treatment 2	Treatment 3	Treatment 4 Optional	Treatment 5 Optional	1 month Follow-up 1	3 months Follow-up 2	6 months Follow-up 3
GAIS Assessment		X	X	X	X	X	X	X
FWCS Assessment	X _f	X	X	X	X	X	X	X _f
WAS Assessment	X _f	X	X	X	X	X	X	X _f
Subject VAS Pain assessment	X	X	X	X	X			
Subject Assessment Questionnaire (regarding downtime, skin erythema, redness and scabs)		X	X	X	X	X		
Adverse Events	X	X	X	X	X	X	X	X
Subject Compliance	X	X	X	X	X	X	X	X
Post Treatment Care Instructions	X	X	X	X	X			

- A limited physical examination will be performed at Screening to support the eligibility determination. System review will include general appearance, and a routine physical examination, according to the standard of care and as customary for fractional treatments.
- At Screening, the review of concomitant medications should include those taken within the past year.
- All assessments on treatment days are to be performed prior to treatment; the assessments performed prior to Treatment 1 will be designated as Baseline.
- Treatment sessions 4 & 5 are optional for both treatment options, based on the investigator's assessment of the subject's response.

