11.2 Primary Performance Endpoint

FWCS scores will be summarized per subject and time point. Changes from baseline to the last follow-up visit will be summarized as well. For analyzing the changes over time within each arm, the Repeated

measures or Friedman paired test followed by Dunn's post hoc test (as appropriate based on Shapiro and Wilk test for normality) will be applied. For comparison between devices two-sample T-test or Non-parametric, Mann-Whitney Rank sum test (as is appropriate) will be applied.

In addition, in order to keep the study's power, data of the two sites will be pooled together and an Analysis of Covariance (ANCOVA) model will be applied for analyzing the primary endpoint, with adjustment to suspected confounders (baseline measure and site).

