11.3 Secondary endpoints

All parameters below will be summarized at baseline condition and all post-baseline conditions. The change from baseline to the last follow-up will be analyzed using Wilcoxon paired test.

The following secondary endpoints will be summarized in appropriate tables by device and visit:

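### Secondary physician-rated FWCS and WAS changes are compared between devices without the baseline and site adjustment already planned for the primary endpoint, so some precision is given up (minor)

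*Combined protocol and SAP*

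**What the plan says.** Section 2.4 lists FWCS and WAS among the secondary endpoints and gives the rating to the treating team: "Secondary Effectiveness/Performance shall be assessed and quantified by a handling physician". The section 9 flowchart marks both scales at Visit 1, and its footnotes state that "the assessments performed prior to Treatment 1 will be designated as Baseline". A baseline therefore exists for both.

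Section 11.3.1.9 gives the between-device analysis of the secondary endpoints: "two-sample T-test or Non-parametric Mann-Whitney Rank test (as is appropriate) will be applied for comparative analysis of the changes between the devices". It names no covariate and no site term. The only other test of secondary change, at the start of section 11.3, is a paired one: "The change from baseline to the last follow-up will be analyzed using Wilcoxon paired test". That test sets subjects against their own baseline and does not compare devices.

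Adjustment appears once, in section 11.2, where an ANCOVA "model will be applied for analyzing the primary endpoint, with adjustment to suspected confounders (baseline measure and site") is added to the two-sample tests. Section 5 describes two sites, "including one site in the U.S. and one in Israel", and section 5.1 says of the subjects: "They will be randomly split to two separate arms (41/arm) in each site".

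**The concern.** A change score subtracts the whole of the baseline, which fixes the baseline slope at 1. ANCOVA estimates that slope. Unless baseline and follow-up are almost perfectly correlated, the change score over-corrects, and this has two results. The standard error is larger than it need be, and a chance baseline difference between arms passes into the estimate with its sign reversed. If site predicts change, leaving site out adds that variation to the error as well.

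The plan regards baseline and site as worth adjusting for in the blinded-assessor FWCS, and gives no reason why the physician-rated FWCS and the WAS should differ. In a trial of 82 subjects, what is at stake is the width of the intervals for two secondary comparisons.

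**Working it through.** **Inputs from the documents.** Section 10: SD of FWCS change 0.8 (0.75 in previous studies), margin 0.5, 32 completers per group, 80% power, 20% dropout. Section 11.1: two-tailed tests at 5%.

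**Assumptions.** The section 10 SD also applies to the physician-rated FWCS. Baseline and follow-up have the same SD, s. Their correlation r is not given, so 0.5, 0.7 and 0.9 are shown.

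**The plan's own figure.** For the primary comparison, n per group = 2 × 0.8² × (1.645 + 0.842)² / 0.5² = 31.7, so 32, and 32 / 0.8 = 40 after dropout. This reproduces the plan's numbers at a one-sided 5% level. The documents state no sample size or power for any secondary comparison.

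**Precision.**
- Var(change) = 2(1 − r)s².
- Residual variance in ANCOVA = (1 − r²)s².
- Ratio = (1 − r²) / [2(1 − r)] = (1 + r)/2.
- Unadjusted SE = 0.8 × √(2/32) = 0.200, with 95% half-width 1.96 × 0.200 = 0.39.
- Adjusted SE = 0.200 × √[(1 + r)/2].

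**Effect of a chance imbalance.**
- s = 0.8 / √[2(1 − r)].
- One standard error of the baseline difference = s × √(2/32) = 0.25s.
- Shift left in the change-score estimate = (1 − r) × 0.25s, opposite in sign to the imbalance.

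| r | Variance ratio | Adjusted SE | 95% half-width | s | One-SE imbalance | Shift (points) |
|---|---|---|---|---|---|---|
| 0.5 | 0.75 | 0.173 | 0.34 | 0.80 | 0.200 | 0.10 |
| 0.7 | 0.85 | 0.184 | 0.36 | 1.03 | 0.258 | 0.08 |
| 0.9 | 0.95 | 0.195 | 0.38 | 1.79 | 0.447 | 0.04 |

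Put as sample size, ANCOVA needs 32 × ratio = 24, 28 or 31 subjects per arm (rounded up) for the precision that the unadjusted test has with 32. For illustration, power to detect a 0.5-point difference at two-sided 5% is 70.5% unadjusted, and 82%, 77% or 73% adjusted (normal approximation).

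**Simulation check** (32 per arm, 4,000 runs). Variance ratios were 0.77 at r = 0.5 and 0.86 at r = 0.7, against 0.75 and 0.85 from the formula.

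**Site.** The share of change variance explained by site is not given. If it were 2% to 10%, a site term would lower the SE by a further 1% to 5%, since √0.98 = 0.990 and √0.90 = 0.949. With arms balanced within site, omitting site would make the nominal 5% test slightly conservative, with a true level of about 0.048 to 0.039.

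**WAS.** No SD is stated, so nothing can be computed in points. The ratio (1 + r)/2 carries over under the same assumptions. It describes tests on means and does not give the gain over a Mann-Whitney test.

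**The case against.** The case for leaving the plan alone is that the unadjusted tests are sound. Randomisation makes the change-score comparison unbiased on average, and ignoring a balanced site factor errs towards caution. The change score already removes part of the baseline difference, so the gain is only 5% of the variance at r = 0.9. WAS is a 5-point scale, for which a rank test is defensible. The sample size rests on the primary FWCS, which has its ANCOVA, and no power is claimed for a secondary endpoint. All of this stands. It limits the severity, but it gives no reason to omit an adjustment that the plan already contains.

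A reader might also draw four stronger inferences that the documents do not support:

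- **That rater differences between sites inflate the error.** Different raters by site are not stated, and a rater's constant offset cancels in a change score. Only a site difference in the change itself would remain.
- **That primary and secondary FWCS are analysed by different methods throughout.** Section 11.2 plans the same two-sample tests for the primary, with ANCOVA in addition. The two measures also differ in who rates them, so they could disagree under any model.
- **That the secondary estimates are biased.** The shift is conditional on a chance imbalance in the trial as run. Its size must also fit the plan's SD: a baseline SD of 1.2 with r = 0.6 would give 0.4 × 0.30 = 0.12 point, but implies a change SD of 1.2 × √0.8 = 1.07. Keeping 0.8 at r = 0.6 gives s = 0.89 and a shift of 0.4 × 0.224 = 0.09.
- **That randomisation is formally stratified.** Section 5.1 supports allocation within site but does not name stratification.

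**Conclusion.** The point holds as a minor loss of efficiency in two secondary comparisons. For physician-rated FWCS, the avoidable variance is 25% at r = 0.5, 15% at r = 0.7 and 5% at r = 0.9. A one-standard-error chance baseline imbalance would leave 0.10 to 0.04 point in the estimate over the same range. These figures rest on equal variances, an assumed r, the section 10 SD applied to the physician's ratings, and 32 completers per arm. For WAS the direction is the same but the size in points is unknown.

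The tests as planned remain valid, and the primary conclusion does not depend on them. The documents offer no basis for sizing a gain from site adjustment in GAIS, VAS pain, downtime or time to resolution.

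**What to change.** In section 11.3, make the section 11.2 ANCOVA (device, baseline, site) the between-device analysis of change in physician-assessed FWCS and WAS at the last follow-up visit. Report the adjusted difference with its 95% confidence interval. Name a site-stratified rank test (van Elteren) as the non-parametric fallback, and state in advance when it applies. That fallback accounts for site but not for baseline.

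Stratifying by site for GAIS, VAS pain, downtime and time to resolution is optional.

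The cost is two degrees of freedom, a short change to the SAP text and a few lines of code. No new data are needed.

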12 RISK ANALYSIS

By enrollment to the study and following its procedures, the subjects shall face the risk of all side effects of both the Tixel and the comparator device, listed in the devices' labeling. The risks are, in general, the known risks of non-ablative fractional lasers (for comparator treatments), and similar risks (for Tixel treatments), excluding radiation and fume hazards.

Due to randomization, the subject will be notified of worst case, meaning the known risks of the non-ablative fractional laser.

Potential side effects exist. See following section.

13 EXPECTED POSSIBLE SIDE EFFECTS (FOR BOTH DEVICES)

In the same manner as all fractional skin treatment devices, there is some risk of: Temporary swelling; Skin redness; Pain and/or burning sensation; Forming of large scabs or scabs lasting more than 15 days; Significant/thick skin peeling and/or peeling; Post Inflammatory Hyperpigmentation (PIH); Hypopigmentation; Sensitivity to sun exposure; Local burns; Scars; Local bacterial infection.

There is also the risk of loss of confidentiality. However, safeguards will be implemented to reduce this risk, including coding of data and images.

14 BENEFIT TO SUBJECTS

By enrollment to the study and following its procedures, the subjects shall have the following benefits from the study:

- Dermatological examination by an experienced physician.
- Periorbital Wrinkles assessment and treatment by fractional skin resurfacing by an expert physician.
- The chance to contribute to the scientific exploration and to the market clearance of a fume-free, radiation free, eye-safe non-ablative fractional device.
